7.6 Description of Subgroups to be Analyzed

No subgroup analyses are planned.

7.7 Statistical Analysis Methodology

Before unblinding, a separate SAP will be finalized, providing detailed methods for all endpoints. In general, summary statistics (n, mean, standard deviation, median, minimum and maximum values for continuous variables, and number [%] of subjects in each category for categorical variable) will be provided by treatment group and visit. Source data for summary tables and statistical analyses will be presented as subject data listings.

All statistical analyses will be performed using SAS (v9.4 or higher). Unless stated otherwise, all statistical tests will be 2-sided using a 5% significance level, leading to 95% (2-sided) confidence intervals. No adjustment will be made for multiplicity due to 2 dose levels of GTx-024 being compared with placebo. The trial is not powered to show a statistical difference between the 2 dose arms of GTx-024.

The primary efficacy period is defined as baseline (Day 0) through Week 12. Change from baseline and determination of responder rate status will be between baseline and visits through Week 12. The durability period is defined as Week 12 to Week 16, Week 20, and/or Week 28.

7.7.1 Analysis of the Primary Efficacy Endpoint

The primary analysis will be conducted on the primary endpoint using the FAS.

The primary efficacy endpoint (i.e., a binary response indicator where a responder is defined as having a $\geq 50\%$ reduction at the end of treatment compared to baseline in the mean number of stress incontinence episodes per day as assessed by the 3-day voiding diary) will be evaluated using a logistic regression model. The logistic regression model will include treatment group as a covariate. The odds ratio of response between each dose level of GTx-024 and placebo (together with the corresponding 95% confidence interval) will be reported. The null hypothesis is that there is no treatment effect for either dose level of GTx-024. This will be tested against the alternative hypothesis that there is a treatment effect for at least 1 of the dose levels of GTx-024.

The corresponding *P*-value for the comparison between each dose level of GTx-024 and placebo will be derived using the standard normal distribution. Subjects who have missing diary data for the screening period or the Week 12 visit will be counted as non-responders for this analysis.

Sensitivity analyses will be specified in the SAP.

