4.1.1 Inclusion Criteria

Each subject must meet all of the following criteria to be enrolled in this study:

1. Able to read, understand, and provide written, dated, informed consent prior to screening, and be likely to comply with study protocol and communicate with study personnel about AEs and other clinically important information.
2. Female, 18 to 80 years of age, inclusive, at screening
3. Subjects must have undergone spontaneous, medically induced, or surgical menopause prior to the start of this study. Postmenopausal subjects are defined as those subjects who meet one of the following criteria:
 - a) greater than or equal to 12 months of spontaneous amenorrhea, or;
 - b) at least 6 months of spontaneous amenorrhea with serum follicle stimulating hormone levels > 40 mIU/ml, or;
 - c) at least 6 weeks postsurgical bilateral oophorectomy with or without hysterectomy, or;
 - d) subjects 60 years of age or older with previous hysterectomy without an oophorectomy with serum follicle stimulating hormone levels > 30 mIU/ml, or;
 - e) subjects less than 60 years of age with previous hysterectomy without an oophorectomy with serum follicle stimulating hormone levels > 40 mIU/ml.
4. SUI symptoms of at least 6 months duration

5. Predominant SUI as determined at the Screening Visit using the MESA incontinence questionnaire.
6. 24-Hour pad weight > 3 g during the screening period
7. A minimum of 1 and no more than 15 SUI episodes on any single day AND no fewer than 9 total SUI episodes over 3 days as reported in the 3-day voiding diary, determined during the screening period
8. Serum alanine aminotransferase (ALT) or aspartate aminotransferase (AST) levels < 1.5 times the upper limit of normal at the Screening Visit (Note: laboratory values falling outside of prespecified ranges may be retested once at the discretion of the investigator. Results of the retest must be within prespecified ranges and must be available prior to the baseline visit)
9. Positive bladder stress test (BST) conducted during the Screening Visit
10. Subject agrees not to start any new treatment (medication or otherwise) during the treatment and follow-up periods, including vaginal rejuvenation, that is known or suspected to affect lower urinary tract function.
11. Subject agrees to discontinue use of bladder support devices, including but not limited to vaginal pessary, during the screening, treatment, and follow-up periods.

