7.7.2 Analysis of Secondary Efficacy Endpoints

For binary secondary endpoints (responders), the treatment effect will be estimated using a logistic regression model with treatment as a covariate.

For continuous secondary endpoints, treatment effects will be estimated using a mixed model repeated measures analysis (MMRM). The MMRM model will specify an unstructured variance/covariance matrix and include treatment group, visit, and baseline as covariates.

For ordinal endpoints, treatment effects will be estimated using a proportional odds model.

Further details on the analysis of secondary efficacy endpoints will be provided in the SAP.

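### The responder models adjust for treatment only; prespecifying baseline severity would be a modest gain in efficiency and robustness, not the correction of an error

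*Combined protocol and SAP*

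**What the plan says.** - **Primary endpoint (7.7.1).** Response is a reduction of at least 50% from the subject's own baseline in mean stress episodes per day. On the model: "The logistic regression model will include treatment group as a covariate". No other term is listed. An odds ratio with 95% confidence interval is reported for each dose, and sensitivity analyses are left to a separate SAP.
- **Binary secondary endpoints (7.7.2).** "For binary secondary endpoints (responders), the treatment effect will be estimated using a logistic regression model with treatment as a covariate".
- **Continuous secondary endpoints (7.7.2).** "The MMRM model will specify an unstructured variance/covariance matrix and include treatment group, visit, and baseline as covariates".
- **Ordinal endpoints (7.7.2).** "For ordinal endpoints, treatment effects will be estimated using a proportional odds model". No covariates are listed, and further detail is deferred to the SAP.
- **Baseline data.** Inclusion criterion 7 (4.1.1) requires "no fewer than 9 total SUI episodes over 3 days as reported in the 3-day voiding diary, determined during the screening period"; criterion 6 requires a 24-hour pad weight above 3 g. Section 6.1.2 has both results reviewed at Visit 1 before randomization. PGI-S is also completed at Visit 1.
- **Missing baseline (7.7.1).** "Subjects who have missing diary data for the screening period or the Week 12 visit will be counted as non-responders for this analysis".
- **Randomization (5.1).** 1:1:1, with no stratification factor named.

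**The concern.** Severity at entry is a natural candidate predictor of outcome, and it is measured on every eligible subject before allocation. The primary model does not use it, and neither the randomization nor the analysis as described guards against the arms differing in severity by chance. If severity predicts reaching a 50% reduction, two things are given up: some power for each dose against placebo, and the ability to remove a chance imbalance from the estimated effect. The protocol gives no reason for leaving baseline out. Covariates chosen after unblinding would look data-driven, so the decision has to be made beforehand.

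**Working it through.** **1. The plan's own sample size.** Inputs from 7.4: 60% vs 40%, two-sided 5%, 80% power, 25% discontinuation, three equal arms. With pooled variance and no continuity correction:

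n = [1.96·√(2·0.5·0.5) + 0.8416·√(0.6·0.4 + 0.4·0.6)]² / 0.20² = 96.9, so 97 per arm.

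97 / 0.75 = 129.3, so 130 per arm; 3 × 130 = 390, in line with the stated figure of approximately 400. The plan was sized on an unadjusted comparison and does not rely on covariates.

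**2. Power with and without a baseline covariate.** The documents give no figure for the association between baseline severity and response, so it is an assumption here: a log odds ratio of 0 to 1.0 per SD of a standardized baseline covariate. Three-arm trials were simulated (6,000 per setting) with marginal response rates held fixed, using a Wald test of one dose against placebo. Two scenarios bound the handling of dropouts:

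- (a) 100 completers per arm, 60% vs 40%.
- (b) 133 per arm, with 25% dropout in every arm counted as non-response: 0.75 × 60% = 45% and 0.75 × 40% = 30%. This assumes that all dropouts are in the full analysis set. The 45% and 30% rates are derived and do not stand in the protocol.

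| Log OR per SD | (a) treatment only → adjusted | Change | (b) treatment only → adjusted | Change |
|---|---|---|---|---|
| 0 | 82.0 → 80.9% | -1.1 | 71.3 → 71.2% | -0.1 |
| 0.2 | 82.5 → 81.6% | -0.9 | 72.4 → 72.5% | +0.1 |
| 0.4 | 82.7 → 82.4% | -0.3 | 72.0 → 73.7% | +1.7 |
| 0.6 | 82.9 → 84.0% | +1.1 | 70.6 → 73.8% | +3.2 |
| 0.8 | 83.0 → 85.8% | +2.8 | 72.5 → 77.6% | +5.1 |
| 1.0 | 82.2 → 87.7% | +5.5 | 71.9 → 78.9% | +7.0 |

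Monte Carlo error is about 0.5 point per entry, so compare within rows. Closed-form unadjusted power is 81.2% in (a) and 71.7% in (b).

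**3. Validity of the treatment-only test.** With 40% response in both arms and 100 per arm (8,000 trials; log OR per SD 0, 0.4 and 0.8), type I error was 5.1 to 5.4% unadjusted and 5.0 to 5.1% adjusted.

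**4. What adjustment does to the estimate.** In (a), the SE of the log odds ratio is 0.290 unadjusted. Adjusted, it is 0.298, 0.313 and 0.324 at log OR per SD of 0.4, 0.8 and 1.0. The adjusted log odds ratio moves from about 0.82 to 0.85, 0.94 and 0.99. Power rises when the estimate grows faster than its SE. The odds ratio itself does not become more precise. A standardized risk difference does: at 100 per arm, its variance relative to the unadjusted difference was 1.01, 0.99, 0.94 and 0.89 at log OR per SD of 0, 0.25, 0.5 and 0.75, and a little above 0.8 at 1.0.

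**5. Chance imbalance.** With 100 per arm, the SD of the standardized baseline difference is √(2/100) = 0.141. An imbalance of 1.96 SDs is 1.96 × 0.141 = 0.277. It shifts a 40% placebo rate by roughly 0.24 × log OR × 0.277. Computed exactly, the shift is 1.3, 2.6 and 3.7 points at log OR per SD of 0.2, 0.4 and 0.6, against a planning difference of 20 points.

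**6. How prognostic the diary count might be.** A simple gamma-Poisson/negative-binomial diary model with entry at 9 or more episodes gave slopes of -0.04 to 0.25 per SD of log baseline count, the weak end of the table. This comes from an assumed model, not from trial data.

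**The case against.** **The unadjusted analysis is valid, and baseline already enters the outcome.** Both stand. Type I error is held, the sample size was built on the same unadjusted comparison, and a percentage reduction already uses the subject's own baseline. If the count is as weakly prognostic as the simple diary model suggests, the power change is about zero.

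**A reader might infer that the plan contradicts itself,** because its MMRM does "include treatment group, visit, and baseline as covariates". It does not. The MMRM handles continuous outcomes such as change in episodes per day, where change depends on the starting level. The responder outcome is already relative to baseline. Different covariates for different endpoint types are a choice, not an inconsistency.

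**A reader might also infer that the primary odds ratio loses precision.** It does not: adjustment raises the SE of the log odds ratio. Gains are in power and in the precision of a standardized risk difference, which the plan does not currently report.

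**Adjustment is not free of consequences.** This stands. Section 7.7.1 provides for missing screening diaries and counts those subjects as non-responders. A standard adjusted fit would drop them unless a rule is written. Criteria 6 and 7 should make such cases few.

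**Pad weight is unproven.** This stands. Nothing in the documents shows that pad weight predicts a 50% reduction in episodes, so it is optional.

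**The separate SAP may settle this.** Partly. Section 7.7 defers detailed methods to a SAP whose text is not in the document reviewed, so an omission from the PGI-S model is not established: the ordinal sentence lists no covariates at all. For the primary endpoint, however, 7.7.1 names the covariate itself and defers only sensitivity analyses.

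**Conclusion.** The point holds as a modest improvement to a valid analysis. The responder models use treatment alone, the baseline measures are already collected, and no stratification by severity is named. Power would change by about -1 to +2 points if the log odds ratio per SD is 0 to 0.4, and by about +1 to +7 points at 0.6 to 1.0. Protection against chance imbalance grows in the same way. These ranges rest on an assumed prognostic strength, a normally distributed covariate with a linear effect on the log-odds, and the two dropout scenarios above. The documents do not say where in the range this trial lies, and they do not support a claim of bias, of an invalid test or of an unconditional loss. The argument for acting is that the possible cost is about 1 point of power and the possible gain is several.

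**What to change.** Before unblinding, in 7.7.1 and 7.7.2 or the SAP:

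1. Add log baseline mean stress episodes per day to the primary and binary secondary responder models. Log baseline 24-hour pad weight may be added. Both logs are defined for eligible subjects (at least 9/3 = 3 episodes per day; pad weight above 3 g).
2. State a rule for a missing baseline covariate, such as overall-mean imputation, so that a subject with no screening diary stays in the model as a non-responder, as 7.7.1 requires.
3. Report the standardized (marginal) risk difference with confidence interval for each dose beside the conditional odds ratio, so that the result can be read against the 20-point planning difference.
4. Keep the treatment-only model as a named sensitivity analysis.
5. When the SAP details the PGI-S proportional odds model, include baseline PGI-S: possible change on a 4-point scale is bounded by the starting category.

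**Cost:** wording only, with no new data or visits. The adjusted odds ratio is conditional and has a larger SE, the missing-covariate rule is one more thing to specify, and power may fall by up to about 1 point if baseline turns out not to be prognostic.

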7.7.2 Analysis of Secondary Efficacy Endpoints

For binary secondary endpoints (responders), the treatment effect will be estimated using a logistic regression model with treatment as a covariate.

For continuous secondary endpoints, treatment effects will be estimated using a mixed model repeated measures analysis (MMRM). The MMRM model will specify an unstructured variance/covariance matrix and include treatment group, visit, and baseline as covariates.

For ordinal endpoints, treatment effects will be estimated using a proportional odds model.

Further details on the analysis of secondary efficacy endpoints will be provided in the SAP.

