
Objectives:
	
Primary Objective - Efficacy
 
The primary efficacy objective of this study is to compare the efficacy of GTx-024 (1 mg and 3 mg administered once daily) to that of placebo by evaluating the mean number of subject-reported stress incontinence episodes per day.
 
The primary efficacy endpoint is a responder analysis, where a responder is defined as having a $\geq 50\%$ reduction at the end of treatment (Week 12) compared to baseline in the mean number of stress incontinence episodes per day as assessed by the 3-day voiding diary. Subjects who have missing diary data for the Week 12 visit will be counted as non-responders for this analysis.
 
Secondary Objectives - Efficacy
 
The secondary efficacy objectives in this study are to compare, at each visit during the treatment period, the efficacy compared to baseline of 2 doses of GTx-024 (1 mg and 3 mg administered once daily) to that of placebo in relation to the following:
 
 • Responder rate, where a responder is defined as

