For binary secondary endpoints (responders), the treatment effect will be estimated using a logistic regression model with treatment as a covariate.

For continuous secondary endpoints, treatment effects will be estimated using a mixed model repeated measures analysis (MMRM). The MMRM model will specify an unstructured variance/covariance matrix and will include treatment group, visit, and baseline as covariates.

For ordinal endpoints, treatment effects will be estimated using a proportional odds model.

Further details on the analysis of secondary efficacy endpoints will be provided in the SAP.

Analysis of Exploratory Efficacy Endpoints

Durability of treatment effect will be examined in the DS for the exploratory efficacy endpoints. Additional sensitivity analyses of exploratory and secondary efficacy

	
endpoints may also be conducted as exploratory analyses, including sensitivity analyses with regard to missing data. Further details of the exploratory analyses will be provided in the SAP.
 
Safety Analyses
 
All safety parameters (including AEs, vital signs, laboratory evaluations, SHBG, testosterone, and endometrial stripe thickness) will be summarized using the SA set. No formal hypothesis testing will be performed.
 
All AEs will be coded using the latest version of Medical Dictionary for Regulatory Activities (MedDRA). All treatment-emergent AEs (TEAEs) will be summarized and presented in the listings by the number of subjects reporting an event, the percentage of subjects with that event, the number of events, and the grade, duration, and relationship to treatment. Percentages will be based on the number of subjects who received each treatment during the study.
 
Clinical laboratory safety tests will be performed, and normal ranges will be provided for each lab test. Values outside the normal range will be assessed for clinical significance by the investigator. Shift tables (change from baseline value to on-treatment values) will be presented for each laboratory measurement and assessment time. Each parameter outside the normal range will be designated as high (H) or low (L) in the individual data listings.

--	---

List of Abbreviations

Abbreviation	Definition
AE	adverse event
ALT	alanine aminotransferase
AST	aspartate aminotransferase
BST	bladder stress test
CFR	Code of Federal Regulations
DS	durability set
ECG	electrocardiogram
eCRF	electronic case report form
FAS	full analysis set

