2.2 Secondary Objectives

The secondary efficacy objectives in this study are to compare, at each visit during the treatment period, the efficacy compared to baseline of two doses of GTx-024 (1 mg and 3 mg administered once daily) to that of placebo in relation to the following:

- Responder rate, where a responder is defined as having a $\geq 50\%$ reduction compared to baseline in the mean number of stress incontinence episodes per day as assessed by the 3-day voiding diary
- Change in the number of stress incontinence episodes per day as measured by the 3-day voiding diary
- Change in the total number of voids per day as measured by the 3-day voiding diary
- Change in 24-hour pad weight as measured by the 24-hour pad weight test
- Change in the Bladder Stress Test (BST) (at Week 12 only)
- Change in subject-reported impression of SUI severity as measured by the Patient Global Impression of Severity scale (PGI-S)
- Change in subject-reported impression of SUI improvement as measured by the Patient Global Impression of Improvement scale (PGI-I)
- Change in subject-reported urogenital distress as measured by the Urinary Distress Inventory questionnaire (UDI-6)

- Change in subject-reported impact of urinary incontinence on daily life as measured by the Incontinence Impact Questionnaire (IIQ-7) Short Form
- Change in subject-reported impact of urinary incontinence on daily life as measured by the Incontinence Quality of Life questionnaire (I-QOL)
- Change in subject-reported sexual function as measured by the Female Sexual Function Index questionnaire (FSFI)
- Change in subject-reported assessment of fecal incontinence as measured by the Vaizey Incontinence Severity Score
- Change in subject-reported stress incontinence, urge incontinence, and mixed incontinence as measured by the Medical, Epidemiological, and Social Aspects of Aging (MESA) incontinence questionnaire (Week 12 only)

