7.2 Secondary Efficacy Endpoints

The secondary efficacy endpoints in this study are the following assessments compared to baseline at each visit during the treatment period:

- Responder rate, where a responder is defined as having a $\geq 50\%$ reduction compared to baseline in the mean number of stress incontinence episodes per day as assessed by the 3-day voiding diary
- Change in the number of stress incontinence episodes per day as measured by the 3-day voiding diary
- Change in the total number of voids per day as measured by the 3-day voiding diary
- Change in the mean number of stress incontinence episodes per day as measured by the 3-day voiding diary
- Change in 24-hour pad weight as measured by the 24-hour pad weight test
- Change in the results of the Bladder Stress Test (BST)
- Change in subject-reported impression of SUI severity as measured by the PGI-S
- Change in subject-reported impression of SUI improvement as measured by the PGI-I
- Change in subject-reported urogenital distress as measured by the UDI-6
- Change in subject-reported impact of urinary incontinence on daily life as measured by the IIQ-7 Short Form

- Change in subject-reported impact of urinary incontinence on daily life as measured by the I-QOL
- Change in subject-reported sexual function as measured by the FSFI
- Change in subject-reported assessment of fecal incontinence as measured by the Vaizey Incontinence Severity Score.
- Change in subject-reported stress incontinence, urge incontinence, and mixed incontinence as measured by the MESA incontinence questionnaire (Week 12 only)

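### The mixed model for continuous secondary endpoints has no treatment-by-visit term, so as written it cannot give the by-visit comparisons with placebo that the secondary objectives call for

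*Combined protocol and SAP*

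**What the plan says.** Section 7.7.2 assigns the continuous secondary endpoints to a mixed model for repeated measures (MMRM) and lists its terms: "The MMRM model will specify an unstructured variance/covariance matrix and include treatment group, visit, and baseline as covariates". The synopsis repeats the list: "The MMRM model will specify an unstructured variance/covariance matrix and will include treatment group, visit, and baseline as covariates". Neither place names a treatment-by-visit term or says which contrasts will be reported.

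The secondary objectives in section 2.2 are to "compare, at each visit during the treatment period, the efficacy compared to baseline of two doses of GTx-024", and the comparator is explicit: "efficacy compared to baseline of two doses of GTx-024 (1 mg and 3 mg administered once daily) to that of placebo". The synopsis objectives read the same way. Section 7.2 defines the endpoints as the "following assessments compared to baseline at each visit during the treatment period", without itself naming placebo. Section 3.1 puts the treatment-period clinic visits after baseline at Weeks 4, 8 and 12.

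Section 7.7 adds that summary statistics "will be provided by treatment group and visit" and that "Before unblinding, a separate SAP will be finalized, providing detailed methods for all endpoints". Section 7.7.2 likewise leaves further details of the secondary analyses to the SAP.

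**The concern.** A model with treatment, visit and baseline as main effects forces the dose-minus-placebo difference to be the same at every visit. The unstructured covariance does not relax this. It only decides how much each visit contributes to the one estimate. The objective asks for three differences per dose (six in all) and the model supplies one per dose (two in all).

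If the effect is still developing between Weeks 4 and 12, which a 12-week course of a drug acting through muscle makes plausible, the single estimate need not equal the effect at Week 12 or at any other visit. What is lost is the baseline-adjusted difference from placebo, with its confidence interval, at each visit. The endpoints concerned are those treated as continuous and measured repeatedly, for example episodes per day, voids per day, pad weight and questionnaire scores.

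**Working it through.** **The plan's own figures.** The plan gives no numerical value for these endpoints. Its sample size concerns the primary responder endpoint only. With 60% versus 40%, two-sided 5% and 80% power, the usual two-proportion formula gives 97 per arm; 97/0.75 is 130 after rounding up, and 3 × 130 = 390, consistent with about 400. Nothing below changes it.

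**What the stated model estimates.** Let d be the vector of dose-minus-placebo differences at Weeks 4, 8 and 12, and S the within-subject covariance. A single treatment coefficient fitted by generalized least squares to complete data is

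τ = w′d, with w = S⁻¹1 / (1′S⁻¹1).

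The weights sum to 1. They depend on S, not on which visit matters clinically.

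**Assumed inputs.** All are assumptions, since the documents give none.
- Effects versus placebo at Weeks 4/8/12: steep 0.5/1.0/1.5, or near-plateau 1.2/1.5/1.5.
- Correlation: compound symmetry (CS) 0.4, 0.6, 0.8; AR(1) 0.5, 0.7.
- SDs: equal, falling 2/1.75/1.5, or rising 1.5/1.75/2.

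**Examples.**
- Equal SDs, CS: weights 1/3 each. Steep: (0.5 + 1.0 + 1.5)/3 = 1.0 against 1.5 at Week 12, or −33.3%. Near-plateau: (1.2 + 1.5 + 1.5)/3 = 1.4 against 1.5, or −6.7%.
- Rising SDs, CS 0.6: weights 0.652, 0.282, 0.066. Steep: 0.326 + 0.282 + 0.099 = 0.707, or −52.9%.

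**Week 12 error, complete data (steep | near-plateau).**

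| Correlation | Equal SDs | Falling SDs | Rising SDs |
|---|---|---|---|
| CS 0.4 | −33.3% \| −6.7% | −20.9% \| −3.3% | −45.7% \| −10.7% |
| CS 0.6 | −33.3% \| −6.7% | −13.8% \| −1.3% | −52.9% \| −13.0% |
| CS 0.8 | −33.3% \| −6.7% | +5.1% \| +3.8% | −71.7% \| −19.2% |
| AR(1) 0.5 | −33.3% \| −8.0% | −22.1% \| −4.9% | −44.6% \| −11.7% |
| AR(1) 0.7 | −33.3% \| −8.7% | −16.1% \| −4.0% | −50.5% \| −14.4% |

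The extremes, +5.1% and −71.7%, arise only at CS 0.8 with unequal SDs, where one visit has weight −0.19. In the other 13 cases all weights are positive, and the ranges are −13.8% to −52.9% (steep) and −1.3% to −14.4% (near-plateau).

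**Discontinuation.** Section 7.4 anticipates about 25% overall but gives no timing. S⁻¹ is replaced by the average, over dropout patterns, of the inverse covariance of the visits observed. Loss is taken as equal across arms and unrelated to outcome. Equal-SD errors over the five correlation structures:

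| Assumed timing of the 25% | Steep | Near-plateau |
|---|---|---|
| 12.5% after Week 4, 12.5% after Week 8 | −37.8% to −39.1% | −8.1% to −9.9% |
| All before Week 4 | −33.3% | −6.7% to −8.7% |
| All after Week 4 | −38.9% to −40.8% | −8.9% to −10.9% |
| All after Week 8 | −36.8% to −37.4% | −7.4% to −9.0% |

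**Simulation check.** With 133 per arm, 25% monotone dropout, correlation 0.5, SDs 0.8/1.0/1.2 and true differences −0.25/−0.50/−0.75, the model as written returned the single value −0.332. With treatment-by-visit added it returned −0.255/−0.492/−0.740.

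**The case against.** The strongest reply is that section 7.7.2 is an outline. A separate SAP, due before unblinding, is to give the detailed methods and may well include the interaction. It can be added that the text says the model will include three covariates, not that it will contain only those, so the list may be incomplete. The SAP point limits what can be claimed: the finding is about the protocol text, not a prediction that by-visit contrasts will be missing from the report. The reading of an incomplete list is weak. The text fixes both the covariance structure and the terms, gives the same list twice, and read literally has no interaction.

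The percentages also rest on assumed effect shapes, SDs and correlations, and on scoring against Week 12, although the objective says each visit and singles out none for these endpoints. The timing of discontinuation is assumed, and the protocol does not say to which visit the early-withdrawal assessments at Visit 5 are assigned. All of this stands: the figures show what can happen, not what is likely here.

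Finally, the consequence is bounded. These are secondary endpoints in a Phase 2 trial. Unadjusted by-visit summaries and the by-visit responder analysis remain, and the averaged contrast is a valid test of no effect at any visit. None of this supplies the adjusted by-visit contrasts that section 2.2 asks for.

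**Conclusion.** The point holds: the model is wrong as written for its stated objective. That a main-effects model yields one difference per dose is algebra and needs no assumption. The size of the discrepancy does. It is zero for a flat effect. With complete data and equal SDs it is about 7% to 9% at Week 12 for a near-plateau effect, and one third for an effect that triples between Weeks 4 and 12. Unequal SDs can make it smaller or larger. The protocol should be corrected, but the defect does not reach the primary analysis, the responder and ordinal analyses, the Week 12-only items (BST and MESA) or the sample size.

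**What to change.** In section 7.7.2 and the synopsis, give the fixed effects as treatment group, visit, treatment-by-visit and baseline, with unstructured covariance. State that each dose-minus-placebo least-squares mean difference will be reported with its 95% confidence interval at Weeks 4, 8 and 12. Carry the same text into the SAP before unblinding. A visit-averaged contrast can still be reported from this model. If a visit-averaged effect is what the sponsor wants, amend section 2.2 and the synopsis objectives to say so instead.

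The cost is one line of text and (3 − 1) × (3 − 1) = 4 fixed-effect degrees of freedom. The Week 12 standard error is also wider than that of the averaged contrast. With equal SDs, compound symmetry ρ and complete data, the ratio is √(3/(1 + 2ρ)): 1.074 at ρ = 0.8, 1.168 at 0.6 and 1.291 at 0.4. With 12.5% lost after Week 4 and 12.5% after Week 8, the ratios are 1.118, 1.249 and 1.403. Over all the assumed correlation structures and SD patterns the ratio runs from 1.014 to 1.527 with complete data and from 1.017 to 1.688 with that discontinuation.
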